## 5. Analysis Objectives

The overall objective of the analysis is to demonstrate that the BDV is a leading marker for infection diagnosis in critically ill subjects. Key questions to be answered are 1) Evaluate the BDV as a marker of infections in critically ill subjects at risk of progressing to severe sepsis and septic shock; 2) To measure variation of BDV with time in critically ill ICU patients progressing to severe sepsis and septic shock among those who agree to participate as research subjects; 3) To determine the magnitude of change of BDV in subjects who subsequently progress to severe sepsis and septic shock; 4) To define variation of BDV in critically ill ICU subjects who do not progress to severe sepsis and septic shock.

The BDV will be analyzed to determine the range of exhaled  $^{13}\text{CO}_2/^{12}\text{CO}_2$  BDV in adult subjects. The  $^{13}\text{CO}_2/^{12}\text{CO}_2$  BDV will be compared with current clinical standard scores, physiologic measurements and biomarkers (e.g. vital signs, WBC, CRP, PCT), and any interventions -- such as antibiotic administration -- will be noted for the purpose of assisting in understanding variation of BDV. For the purpose of defining a positive BDV for the presence of an infection, a positive BDV is defined as a change of greater than 1‰ within a 24-hour period above or below the baseline value. The 1‰ threshold for change in the BDV within 24 hours is based on the variability of approximately 0.5‰ seen in subjects with stable nutrition who do not develop infections. Thus, a change of 2 standard deviations away from the pre-infection mean will be examined as part of sensitivity among those with progression to severe sepsis and septic shock and positive predictive value for progression to severe sepsis and septic shock.

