### Hypotheses

#### Co-Primary Endpoint 1

1. Null hypothesis: BDV sensitivity is more than 10% worse than PCT sensitivity for progression to severe sepsis and septic shock in critically ill adult ICU subjects
2. Alternative hypothesis: BDV sensitivity is less than 10% worse than PCT sensitivity for progression to severe sepsis and septic shock in critically ill adult ICU subjects

#### Co-Primary Endpoint 2

1. Null hypothesis: BDV specificity is more than 10% worse than PCT specificity for those not progressing to severe sepsis and septic shock in critically ill adult ICU subjects
2. Alternative hypothesis: BDV specificity is less than 10% worse than PCT specificity for those not progressing to severe sepsis and septic shock in critically ill adult ICU subjects.

#### Secondary Endpoint 1

1. Null hypothesis: the variability of BDV in critically ill adult ICU subjects does not change after clinical diagnosis of progression to severe sepsis and septic shock.
2. Alternative hypothesis: the variability of BDV in critically ill adult ICU subjects increases after clinical diagnosis of progression to severe sepsis and septic shock.

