## **6. Analysis Sets/Populations/Subgroups**

The first task is to demonstrate that there is a positive signal associated with the Canary test using the subject as their own control.

A per protocol analysis will be performed following EAC event reconciliation and subsequent database lock. The EAC will determine diagnostic truth by documenting severe sepsis or septic shock events as well as the onset and resolution dates.

Infection documentation will be reviewed by the EAC committee based on best clinical practices, using four categories:

- No suspicion of infection
- Inconclusive evidence of infection
- High suspicion of infection
- Overt infection

For sensitivity and specificity, non-inferiority testing will be performed to rule out a -10% disadvantage according to a one-sided 97.5% lower confidence limit for the BDV – PCT

difference; exact McNemar paired comparison tests will be performed to test BDV non-inferiority relative to PCT. Both endpoints must achieve statistical significance in order to achieve study success.

PPV and NPV will be computed as observed and for a range of possible infection prevalence (10%, 20%, 30%, and 40%). Results will be analyzed in the same manner as sensitivity and specificity.

BDV variations will be assessed using a two-sample t-test to compare the averaged (across time points) BDV between subjects who are diagnosed with a severe sepsis and sepsis shock vs. no severe sepsis or sepsis shock. Also a linear mixed effects model with subject specific random effects will be used to compare BDV measurements between the two diagnostic groups. This model will be also used to estimate the intra- and inter-subject variability of the BDV measurements. A paired t-test will be used to compare the BDV measurements prior to and after a diagnosis of infection or sepsis.

The definition of a positive BDV will be based on a 72-hour window without advance knowledge of the diagnosis. In the absence of clinical details supporting PCT operating characteristics (sensitivity, specificity), two PCT thresholds (0.5 and 2.0) will be evaluated but the 0.5 threshold is deemed to be primary for BDV comparison.

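### SAP Secondary Endpoint 1 says BDV variability rises after diagnosis, but no listed analysis tests a before/after change in variability

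*SAP*

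**What the plan says.** In SAP section 5, under Hypotheses, Secondary Endpoint 1 has the null that "the variability of BDV in critically ill adult ICU subjects does not change after clinical diagnosis of progression to severe sepsis and septic shock" and the alternative that "the variability of BDV in critically ill adult ICU subjects increases after clinical diagnosis of progression to severe sepsis and septic shock". It is a directional statement about spread, before versus after a defined event.

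SAP section 6 then lists the analyses of BDV values:
- "BDV variations will be assessed using a two-sample t-test to compare the averaged (across time points) BDV between subjects" with and without severe sepsis or septic shock.
- In addition, "a linear mixed effects model with subject specific random effects will be used to compare BDV measurements between the two diagnostic groups". Of the same model it says: "This model will be also used to estimate the intra- and inter-subject variability of the BDV measurements".
- The single procedure that sets readings before diagnosis against readings after it is this: "A paired t-test will be used to compare the BDV measurements prior to and after a diagnosis of infection or sepsis".

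Section 6 also assigns exact McNemar tests to the sensitivity and specificity comparisons. Section 9 repeats the t-tests and the mixed model, and adds Fisher's exact test and kappa for BDV positivity against diagnosis. For Secondary Endpoint 1 the SAP gives no measure of variability, no before and after windows, no test of variance and no power.

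**The concern.** The endpoint and the listed analyses differ in three ways.

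- **Quantity.** The endpoint is about spread. Averaging a subject's readings over time removes the within-subject spread, and the paired t-test also compares levels.
- **Contrast.** The endpoint is before versus after diagnosis. The two-sample t-test and the mixed model compare diagnosed with undiagnosed subjects.
- **Event.** The only before/after procedure is centred on infection or sepsis. The endpoint is centred on progression to severe sepsis and septic shock.

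If the plan is followed exactly, the secondary hypothesis gets no answer. An analyst who notices would have to choose the measure, windows and test after the data are in. Section 6 also introduces a comparison of averages as the way BDV variations are assessed, which invites confusion between level and spread.

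**Working it through.** **1. Listed procedures against the endpoint**

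| Procedure (SAP 6, 9) | Quantity compared | Before vs after? | Tests spread? |
|---|---|---|---|
| Two-sample t-test | time-averaged BDV | no, between groups | no |
| Mixed model, group effect | BDV level | no, between groups | no |
| Mixed model, variance components | intra- and inter-subject variability | no split stated | estimated, not tested |
| Paired t-test | BDV level | yes, around infection or sepsis | no |
| McNemar, Fisher, kappa | classifications | no | no |

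**2. The one before/after power figure in the documents.** Protocol 7.1 gives 79% power for a mean decrease of 2.0‰, SD of change 1.5‰, 5 infected subjects, one-sided 5%. For a paired t-test the noncentrality is (2.0/1.5) × √5 = 2.98, with 4 df and critical value 2.13. Power is 78.7%, which agrees. With 10 infected subjects the noncentrality is (2.0/1.5) × √10 = 4.22 and power is 98.7%, against 99% stated. The only powered before/after comparison is therefore about level.

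**3. Why a test of means cannot answer the question.** For subject *i* let d_i = mean after − mean before. The paired t-test tests E(d) = 0. If only the SD changes, E(d) stays 0 and the test rejects at its alpha level, however large the change in SD.

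**4. Simulation.** From SAP section 5: intra-subject SD 0.95‰, inter-subject SD 1.0‰. From SAP section 6: two-sided 5%. Assumed: 18 readings per side (72 h ÷ 4 h), lag-1 correlation 0 or 0.5, 10, 40 or 97 diagnosed subjects, a flat level within each window. The comparator is a paired t-test on log(SD after) − log(SD before).

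| Scenario | Paired t-test on means rejects | Paired log-SD test rejects |
|---|---|---|
| SD × 1.5 or × 2, mean unchanged | 4.6–5.5% | 96–100% |
| Mean falls 1 or 2‰, SD unchanged | 99.9–100% | 4.5–5.4% |

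**5. Why the raw SD before diagnosis is not a safe reference.** Step 4 assumes a flat level before diagnosis. The study expects otherwise: protocol 3.0 looks for a fall of about 2.0‰ over 24 h followed by a diagnosis within 72 h. Suppose the fall runs from 48 h to 24 h before diagnosis (assumed timing). Of the 18 four-hourly readings, 7 sit at 0, 5 lie at −1/3 to −5/3, and 6 sit at −2.
- Sum = −5 − 12 = −17. Sum of squares = 55/9 + 24 = 30.11.
- Variance of the level alone = (30.11 − 17²/18)/17 = 0.827.
- With a true SD of 0.5‰, the raw SD before is about √(0.25 + 0.827) = 1.04‰. A true doubling to 1.0‰ then looks like no rise.
- With a true SD of 0.95‰, the raw SD before is about √(0.9025 + 0.827) = 1.32‰. An unchanged SD of 0.95‰ then looks like a decrease.

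Simulation over 10, 20 and 50 subjects, lag-1 correlation 0 or 0.5, and falls starting 48 or 60 h before diagnosis agrees. With a 2‰ fall, a true doubling from 0.5 to 1.0‰ is detected in about 0–2% of trials, a rise from 0.95 to 1.43‰ in 9–83%, and an unchanged SD gives a false decrease in 82–100%. With a 1‰ fall (the SAP threshold), true rises are found in 78–100%, but an unchanged SD of 0.95‰ still gives a false decrease in 13–85%.

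**6. Successive 4-hourly differences under the same 2‰ fall.** Six of the 17 differences gain a step of 1/3‰, which adds 6 × (1/9)/17 = 0.039 to the mean squared difference. At SD 0.5‰ and no serial correlation that quantity is 2 × 0.25 = 0.50, so the measure rises by √(0.539/0.50) − 1 = 4%. At lag-1 correlation 0.5 it is 0.25, and the rise is √(0.289/0.25) − 1 = 8%. The raw SD roughly doubles (1.04/0.5). Differencing greatly reduces the distortion but does not remove it.

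**The case against.** Several arguments on the other side stand.

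- A reader might infer that every analysis compares means and that variability is never measured. The documents do not support that. McNemar, Fisher and kappa compare classifications, and the mixed model does estimate intra- and inter-subject variability. What is missing is a before/after split and a test.
- A reader might infer that the SAP will report a mean shift as proof of rising variability. Section 6 never links its t-tests to Secondary Endpoint 1. Its opening words, "BDV variations will be assessed using a two-sample t-test to compare the averaged (across time points) BDV", could equally serve Objectives 2 to 4, which speak of variation in or magnitude of change of BDV. The supportable finding is that no analysis is assigned; misreporting is a risk, not a plan.
- A reader might take the positivity rule, "a change of greater than 1‰ within a 24-hour period above or below the baseline value", as evidence that readings swing both ways after diagnosis and cancel in the mean. That rule defines a positive test against baseline. It does not describe oscillation after diagnosis, and section 5 also speaks of a sustained change.
- The hypothesis does not say within-subject, and the protocol pairs its variation objective with a hypothesis about BDV level. A level hypothesis may have been intended. Against this, section 5 uses variability for spread when it derives the 1‰ threshold as 2 standard deviations of about 0.5‰. An increase would also run against the fall that the protocol expects. The text needs settling either way.
- The simulated SD rises are assumed, and it is no surprise that a mean test ignores variance. That is fair; the simulation illustrates step 3 rather than adding to it.

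**Conclusion.** The point holds in this form: Secondary Endpoint 1 cannot be answered by any analysis listed in the SAP. This rests on the text and on the fact that a test of means keeps its alpha level under a pure change in variance; it does not depend on the simulation settings. The detection rates for SD-based tests do depend on the assumed readings per window, serial correlation, subject numbers and size of SD change, none of which the documents give.

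This should be fixed before database lock. It is not critical. Section 6 makes study success depend only on the two co-primary endpoints, and this hypothesis carries no power claim or success rule.

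**What to change.** In SAP sections 6 and 9:

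1. Assign Secondary Endpoint 1 a before/after test of within-subject spread around the adjudicated onset of severe sepsis or septic shock. Name the windows and the minimum number of readings per window.
2. Use a measure that does not count drift in level as spread. One option is the planned mixed model with a time trend, serial correlation and separate residual variances before and after diagnosis, compared by a likelihood-ratio test. Another is a paired test of log detrended SD, or of log SD of successive 4-hourly differences. The trend must be flexible enough to follow a fall over about 24 h, and differencing leaves the small residual effect shown above.
3. Do not use the raw SD over the 72 h before diagnosis as the reference.
4. Label the t-tests of BDV as analyses of level.
5. Reconcile the directional alternative with the section 6 rule that all testing is two-sided at 0.05.
6. If a change in level was meant, restate the hypothesis that way and align its event with that of the paired t-test.

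The cost is SAP text and a little more analysis work. The 4-hourly readings are already planned. The downside is fewer usable subjects where readings are missing or a window is short.

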## **6. Analysis Sets/Populations/Subgroups**

The first task is to demonstrate that there is a positive signal associated with the Canary test using the subject as their own control.

A per protocol analysis will be performed following EAC event reconciliation and subsequent database lock. The EAC will determine diagnostic truth by documenting severe sepsis or septic shock events as well as the onset and resolution dates.

Infection documentation will be reviewed by the EAC committee based on best clinical practices, using four categories:

- No suspicion of infection
- Inconclusive evidence of infection
- High suspicion of infection
- Overt infection

For sensitivity and specificity, non-inferiority testing will be performed to rule out a -10% disadvantage according to a one-sided 97.5% lower confidence limit for the BDV – PCT

difference; exact McNemar paired comparison tests will be performed to test BDV non-inferiority relative to PCT. Both endpoints must achieve statistical significance in order to achieve study success.

PPV and NPV will be computed as observed and for a range of possible infection prevalence (10%, 20%, 30%, and 40%). Results will be analyzed in the same manner as sensitivity and specificity.

BDV variations will be assessed using a two-sample t-test to compare the averaged (across time points) BDV between subjects who are diagnosed with a severe sepsis and sepsis shock vs. no severe sepsis or sepsis shock. Also a linear mixed effects model with subject specific random effects will be used to compare BDV measurements between the two diagnostic groups. This model will be also used to estimate the intra- and inter-subject variability of the BDV measurements. A paired t-test will be used to compare the BDV measurements prior to and after a diagnosis of infection or sepsis.

The definition of a positive BDV will be based on a 72-hour window without advance knowledge of the diagnosis. In the absence of clinical details supporting PCT operating characteristics (sensitivity, specificity), two PCT thresholds (0.5 and 2.0) will be evaluated but the 0.5 threshold is deemed to be primary for BDV comparison.

Descriptive statistics will be generated for patient characteristics, demographics, and on-study events relating to subgroups (see Section 7.4). For continuous variables, descriptive statistics may include the number of subjects from whom data was used in the calculation, mean, standard deviation, median, minimum, and maximum; frequencies and percentages may be displayed for categorical data.

The predicate marker PCT sensitivity is estimated to be between 64-82% based on a recent review of the published literature (19); PCT sensitivity will be assumed to be 75% for sample size calculations. BDV sensitivity is expected to range between 80-90% based on the proof-of-concept study. The study is designed to have at least 80% power and one-sided 2.5% Type I error. A greater than 10% disadvantage for BDV vs PCT (null hypothesis) is to be tested against a less than 10% disadvantage for BDV vs PCT (alternative hypothesis). As shown in Table 1, this non-inferiority hypothesis can be tested with 97 documented infection events. The BDV advantage vs PCT resulting in a -10% one-sided 97.5% lower confidence bound (CB) is also displayed in Table 1; if the sensitivities are 76.5% for BDV vs 75% for PCT based on 97 pairs of infection events, then the one-sided 97.5% lower CB would be -10%, which would establish BDV non-inferiority relative to PCT.

Table 1: One-sided 97.5% Lower 97.5% Confidence Limit: Sensitivity Paired Differences (simulation)

	Power	N-I
Confidence level, 1-<math>\alpha</math> (one-sided)	0.975	0.975
Expected difference, <math>\pi_T - \pi_S, \Delta_1</math>	0.100	0.015
Proportion discordant, <math>\eta = \pi_{10} + \pi_{01}</math>	0.400	0.315
Proportion both yes, <math>\pi_{11}</math>	0.600	0.600
Lower limit for <math>\pi_T - \pi_S, LL</math>	-0.100	-0.100
Number of simulations	1000	1000
Random seed for simulations	123	123

Power (%)	89	51
n (number of pairs)	97	97

The predicate marker PCT specificity is estimated to be between 56-78% based on a recent review of the published literature (19); PCT specificity will be assumed to be 65% for sample size calculations. BDV specificity is expected to range between 70-80% based on the proof-of-concept study. The study is designed to have at least 80% power and one-sided 2.5% Type I error. A greater than 10% disadvantage for BDV vs PCT (null hypothesis) is to be tested against a less than 10% disadvantage for BDV vs PCT (alternative hypothesis). As shown in Table 2, this non-inferiority hypothesis can also be tested with 97 documented non-infection events. The BDV advantage vs PCT resulting in a -10% one-sided 97.5% lower confidence bound (CB) is also displayed in Table 2; if the specificities are 66.5% for BDV vs 65% for PCT based on 97 pairs of non-infection events, then the one-sided 97.5% lower CB would be -10%, which would establish BDV non-inferiority relative to PCT. A 10% non-inferiority delta with respect to both sensitivity and specificity ensures that the performance of BDV is comparable to PCT, considering the difference in sampling methods and the potentially greater convenience of breath sampling for BDV.

Table 2: One-sided 97.5% Lower Confidence Limit: Specificity Paired Differences simulation)

	Power	N-I
Confidence level, 1-<math>\alpha</math> (one-sided)	0.975	0.975
Expected difference, <math>\pi_T - \pi_S, \Delta_1</math>	0.100	0.015
Proportion discordant, <math>\eta = \pi_{10} + \pi_{01}</math>	0.400	0.315
Proportion both yes, <math>\pi_{11}</math>	0.100	0.100
Lower limit for <math>\pi_T - \pi_S, LL</math>	-0.100	-0.100
Number of simulations	1000	1000
Random seed for simulations	123	123
Power (%)	87	52
n (number of pairs)	97	97

We will also categorize infections per respiratory and non-respiratory infections within our data analysis to determine if there is an impact on the breath delta value.

We will also categorize samples taken from a ventilator versus free-breathing patient for analysis. To assess the impact of collecting samples from the ventilator versus free breathing subjects, we examined breath samples right before and right after ventilator weaning. Eleven of our subjects have been ventilated at the beginning of our study and then extubated at some point during the study. Out of the eleven subjects who had enough data for the analysis, none showed significant changes in BDV after extubation, meaning that there were no differences between ventilated and free breathing values.

All analyses will be conducted under GCP and FDA 21 CFR 812 standards. SAS (SAS Institute, Cary NC) and StatXact (CyTel, Cambridge MA) will be used to conduct all analyses. All statistical testing will be two-sided using a 0.05 p-value to reach statistical significance.

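### The co-primary endpoints are tested against progression to severe sepsis or septic shock, but the event counts, power and PPV/NPV prevalence grid are stated for infection

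*SAP*

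**What the plan says.** **Severe sepsis or septic shock is the condition tested.** In the Hypotheses part of SAP Section 5, the null for co-primary 1 is that "BDV sensitivity is more than 10% worse than PCT sensitivity for progression to severe sepsis and septic shock", and the null for co-primary 2 is that "BDV specificity is more than 10% worse than PCT specificity for those not progressing to severe sepsis and septic shock". SAP Section 6 adds: "The EAC will determine diagnostic truth by documenting severe sepsis or septic shock events". The numbered objectives and the interim rule are also largely framed around progression.

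**Infection is the condition used for design.**
- SAP Section 5 takes equal proportions of infected and uninfected subjects for the sample size. It bases this on a 50% infection rate in the proof-of-concept study, and also quotes a nosocomial infection rate of 6 to 18%.
- For sensitivity, Section 6 says "this non-inferiority hypothesis can be tested with 97 documented infection events". For specificity it says "this non-inferiority hypothesis can also be tested with 97 documented non-infection events".
- Section 6 projects PPV and NPV over infection prevalences of 10, 20, 30 and 40%.
- The BDV positivity rule is introduced in Section 5 with "For the purpose of defining a positive BDV for the presence of an infection".

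The adjudication committee (EAC) also grades infection in four categories. No rule maps these to diseased and non-diseased. SAP Section 9 and protocol Section 7.2 relate a positive BDV to a diagnosis of either infection or sepsis within 72 hours.

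**The concern.** The reference standard decides which subjects enter the sensitivity and specificity denominators, so it decides both co-primary results and study success. The wording of co-primary 2 places every non-progressor, infected or not, among the non-diseased. If BDV does what the sponsor hopes and turns positive in an infected subject who does not go on to severe sepsis, that result is scored as an error.

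Three things follow from the text as it stands:
- The power in Tables 1 and 2 is for infected versus uninfected pairs, not for progression versus non-progression.
- The number of progression events that the study will yield is not stated.
- The prevalence-projected PPV and NPV combine accuracy measured against severe sepsis or shock with a prevalence of infection.

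If this stays open, the target condition could be settled after results are known.

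**Working it through.** **Inputs from the SAP.** Margin 0.10, one-sided 2.5% (z = 1.96), 97 pairs. Power column of Tables 1 and 2: difference d = 0.10, discordant proportion η = 0.40. N-I column: d = 0.015, η = 0.315. PCT sensitivity is 75%. Table 1 implies BDV sensitivity of 0.60 + (0.40 + 0.10)/2 = 85%. PCT specificity is 65%, and adding the 10-point difference gives BDV 75%.

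**Assumptions not in the documents.** A fraction q of infections progresses; 97 infected and 97 uninfected subjects are enrolled; infected non-progressors test positive at the full 85% (BDV) and 75% (PCT); discordance is 0.40 in every group.

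**Step 1: reproduce the SAP.** Power = Φ{(d + 0.10)/√[(η − d²)/n] − 1.96}.
- d = 0.10: SE = √(0.39/97) = 0.0634; 0.20/0.0634 − 1.96 = 1.19; power 88.4% (stated 89% and 87%).
- d = 0.015: SE = √(0.314775/97) = 0.0570; 0.115/0.0570 − 1.96 = 0.06; power 52.3% (stated 51% and 52%).

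The tables are sound for the pairs they describe.

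**Step 2: sensitivity against progression.** Diseased pairs = 97q. At q = 0.5 there are 48.5 pairs: SE = √(0.39/48.5) = 0.0897; 0.20/0.0897 − 1.96 = 0.27; power 61%. Reaching 80% needs 77 pairs, and 77/97 = 0.79.

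**Step 3: specificity among non-progressors.** N = 97 + 97(1 − q). BDV specificity = [97 × 0.75 + 97(1 − q) × 0.15]/N, and PCT specificity = [97 × 0.65 + 97(1 − q) × 0.25]/N. At q = 0.5, N = 145.5; BDV = 80.025/145.5 = 55.0%; PCT = 75.175/145.5 = 51.7%; d = 0.033; SE = √(0.3989/145.5) = 0.0524; power 72%.

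| q | Progression events | Sensitivity power | Non-progressors | Specificity BDV / PCT | Gap (points) | Specificity power |
|---|---|---|---|---|---|---|
| 1 | 97 | 88% | 97 | 75% / 65% | 10.0 | 88% |
| 0.79 | 77 | 80% | 117 | 65% / 58% | 6.5 | 81% |
| 0.7 | 68 | 75% | 126 | 61% / 56% | 5.4 | 78% |
| 0.5 | 48.5 | 61% | 145.5 | 55% / 52% | 3.3 | 72% |
| 0.25 | 24 | 35% | 170 | 49% / 48% | 1.4 | 65% |

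**Step 4: vary the positivity rate at q = 0.5.** If infected non-progressors are positive at 55% on both markers, specificity is 65% versus 58% and power is 89%. If they behave like uninfected subjects (25% BDV, 35% PCT), specificity is 75% versus 65% and power is 97%.

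**Step 5: use the 6–18% infection rate.** With infection rate p, the infected share of non-progressors is w = p(1 − q)/(1 − pq). At q = 0.5, w is 3.1% (p = 0.06) and 9.9% (p = 0.18). With the Step 3 positivity rates, BDV specificity is 73% and 69%, and specificity power with 97 pairs is 86% and 81%.

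**Step 6: enrolment for 97 progression events.** Subjects needed = 97/(pq). At q = 0.5 this is 388 for p = 0.50, 1,078 for p = 0.18 and 3,234 for p = 0.06.

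**Step 7: PPV at 20% prevalence, BDV sensitivity 85%.** With 75% specificity, 0.17/(0.17 + 0.20) = 46%. With the 55% of Step 3, 0.17/(0.17 + 0.36) = 32%.

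**The case against.** **The positivity rule is not itself a contradiction.** A reader might infer that a cut-off introduced for infection cannot serve a sepsis endpoint. The same paragraph of SAP Section 5 goes on to apply the change criterion to sensitivity and PPV for progression, and a cut-off motivated by one condition may be validated against another. This stands, so the point does not rest on the positivity rule.

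**Progression is the SAP's dominant target.** It appears in the key questions, objectives, co-primary and secondary hypotheses, EAC truth and interim rule. A reader might infer that infection must be the right reference standard because Tables 1 and 2 fit it. The documents do not support that: relabelling the tables would be equally consistent. This also stands.

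**The diseased group need not shrink.** Section 6 states the pairs needed and the SAP fixes no total enrolment; the protocol's figure of 100 belongs to a separate calculation in its Section 7.1. With 97 progression events and the same accuracy inputs, Table 1 is unchanged. So the supported complaint is that the enrolment yielding those events is not stated, and the sensitivity losses above apply only if enrolment stops at 97 infected subjects.

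**The specificity loss rests on assumed rates.** Step 4 shows that it can vanish. The PCT inputs come from a cited review whose target condition the SAP does not state. Both markers also face the same truth in a paired test, so the gap suffers less than absolute specificity. It still narrows under the Step 3 assumptions, because BDV is assumed to detect infection more often than PCT.

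**Some infection-based accuracy is already planned.** Section 9 covers infection or sepsis within 72 hours, and PPV/NPV as observed carry no prevalence mismatch. Both are true, but neither removes the mismatch in the co-primary tests or the prevalence grid.

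**Conclusion.** The point holds as an inconsistency in the SAP. The co-primary hypotheses and EAC truth use one condition; the event counts, the 50% split and the prevalence grid use another. On the wording of co-primary 2, infected non-progressors count as non-diseased.

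A reader might infer that the study misses its 80% power outright. The documents do not support that. Under all four assumptions listed in the working, both powers reach 80% once q is about 0.79 or more, and fall to 61% and 72% at q = 0.5 and to 35% and 65% at q = 0.25. At q = 0.5, specificity power runs from 72% to 97% depending on how often infected non-progressors test positive, and the specificity effect is smaller at the 6–18% infection rate. What can be said without assumptions is that the stated power and the projected PPV/NPV are for a different condition from the one tested. This should be settled before infection status is linked to BDV results.

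**What to change.** Name one target condition for both co-primary endpoints and use it throughout SAP Sections 5 and 6. The choice is the sponsor's.

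- **If severe sepsis or septic shock stays primary:** relabel the 97 + 97 as progression and non-progression events; restate the enrolment needed and the power, with a stated assumption for q; use prevalence of severe sepsis or shock in the PPV/NPV grid; and report specificity separately for infected and uninfected non-progressors. The text change is small, but the enrolment may not be (Step 6).
- **If infection becomes primary:** amend both hypotheses and the EAC truth statement, and specify before unblinding to BDV how the four EAC categories map to infected and not infected, including the inconclusive one. Tables 1 and 2 and the prevalence grid then remain valid. This is a change of target condition, not only of wording.

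Either way, report accuracy against the other condition as a secondary analysis. Section 9 already largely plans this, and the EAC is already asked for both severe sepsis or shock events and infection category, so no new data collection is needed.
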